13.1 Extent of Exposure

Subjects will be characterized by a series of treatment periods as defined in Section 10.1. These treatment period definitions are based on attainment of specified vIGA-AD™ values.

The following exposure and compliance parameters will be summarized descriptively:

- Total expected number of days exposed, calculated as the sum of number of days over all treatment periods.
- Total number of doses administered within treatment periods, calculated from the subject dose diary including in-clinic dosing and summed over all treatment periods. If a subject returns no diary records, then the number of home doses is assumed to be 0. If a subject has no clinic visits where study drug was administered, then the number of clinical doses is assumed to be 0.
- Percent compliance will be calculated as the (total number of doses administered within treatment periods) / (total expected number of days exposed) * 100.
- Subject compliance, defined as $\geq 80\%$ compliance while enrolled in the study. If the percentage of study medication compliance cannot be computed, the subject is assumed to be less than 80% compliant.

In addition, the following exposure parameters will be summarized descriptively for the entire study (regardless of vIGA-AD™ status):

- Total number of doses administered, calculated from the subject dose diary and in-clinic dosing. If a subject returns no diary records, then the number of home doses is assumed to be 0. If a subject has no clinic visits where study drug was administered, then the number of clinical doses is assumed to be 0.
- Grams (g) of study drug administered. Drug administered is calculated as the summation of the difference between dispensed weight and returned weight for all returned tubes. Unreturned/unopened tubes will be assumed unused and will be included as 0 grams in the amount drug used calculation. Average grams of study drug administered per dose will be calculated as the total grams / total number of doses administered. Subjects that had no diaries returned will not have average grams per dose reported.

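### Average grams per dose divides grams from all returned tubes by documented doses only, so it is inflated for subjects who lose some on-treatment diaries but return the tubes

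*SAP*

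**What the plan says.** SAP Section 13.1 defines the quantities as follows.

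- **Grams:** "Drug administered is calculated as the summation of the difference between dispensed weight and returned weight for all returned tubes". For tubes that do not come back: "Unreturned/unopened tubes will be assumed unused and will be included as 0 grams in the amount drug used calculation".
- **Doses, whole study:** "Total number of doses administered, calculated from the subject dose diary and in-clinic dosing".
- **Ratio:** "Average grams of study drug administered per dose will be calculated as the total grams / total number of doses administered".
- **Exclusion from the ratio:** "Subjects that had no diaries returned will not have average grams per dose reported".
- **Missing diaries:** "If a subject returns no diary records, then the number of home doses is assumed to be 0". No rule is stated for a subject who returns some diaries and not others.
- **Compliance:** "Percent compliance will be calculated as the (total number of doses administered within treatment periods) / (total expected number of days exposed) * 100". Its denominator is defined so: "Total expected number of days exposed, calculated as the sum of number of days over all treatment periods". A subject is compliant at 80% or more, and one whose percentage cannot be computed is taken to be below 80%.

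Protocol Section 5.4 bases compliance on the diary and has tubes weighed when dispensed and when returned. The Schedule of Assessments (Protocol Table 1) has a diary collected at each of Visits 2 to 13.

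**The concern.** The two halves of grams per dose come from different sources that can go missing separately. A lost diary removes its home doses from the denominator, while the tubes for the same weeks, if returned, keep their full weight in the numerator. The exclusion for subjects with no diaries shows that the plan recognises the ratio fails without diary doses. It protects only the extreme case: a subject with no diaries is left out, while one with a single diary out of 12 is reported.

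Tubes are also easier to recover than diaries. Protocol Section 5.4 asks for forgotten tubes at the next visit, and no matching provision for diaries appears in the public text. For the itch score kept in the same diary, SAP Section 10.4 sets the weekly average to missing when more than three of seven days are absent. For doses, absent pages in effect count as zero.

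At stake is the accuracy of a descriptive exposure table. A few subjects with heavy diary loss could pull up the mean and maximum of grams per dose. The same undercount enters total doses and percent compliance.

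**Working it through.** The plan gives no exposure or compliance figure to reproduce, so its formulas are applied to the nominal schedule.

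**Inputs**

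- Treatment lasts up to 48 weeks, or 336 days (Protocol Section 3.1).
- There are 12 diaries, collected at Visits 2 to 13, and 12 supervised doses, at Baseline and Visits 2 to 12 (Protocol Table 1).
- Clinic-day doses are recorded in clinic and not in the home diary (Table 1 footnote on the itch score). A 28-day interval therefore holds 1 clinic dose and 27 home doses.
- Assumptions: continuous treatment, every dose applied, all tubes returned, the same grams at each dose, and a lost diary contributing no home doses.

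**Full documentation:** 12 × 27 + 12 = 336 doses over 336 days, so compliance is 100% and grams per dose is correct.

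**With j diaries lost:** documented doses = 336 − 27j; inflation of grams per dose = 336 / (336 − 27j); compliance = (336 − 27j) / 336.

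| Diaries lost | Documented doses | Grams per dose, times true value | Compliance |
|---|---|---|---|
| 1 | 309 | 1.09 | 92.0% |
| 2 | 282 | 1.19 | 83.9% |
| 3 | 255 | 1.32 | 75.9% |
| 6 | 174 | 1.93 | 51.8% |
| 11 | 39 | 8.6 | 11.6% |

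**If the matching tubes are lost too:** they count as 0 g, so the ratio is (336 − 28j) / (336 − 27j). This is 308/309 = 0.997 for one interval, 252/255 = 0.99 for three and 168/174 = 0.97 for six. Only in the extreme case of 11 does it fall well below one (28/39 = 0.72).

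**How firm the 80% crossing is**

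- With 337 expected days, three lost diaries give 255/337 = 75.7%. With 28 doses per diary they give 252/336 = 75.0%.
- With k treated intervals, compliance is (28k − 27j) / 28k. One lost of four gives 85/112 = 75.9%, one of five 80.7%, and two of nine 78.6%.
- Visit windows of ±3 days matter. Three separate lost intervals at the 22-day minimum remove 3 × 21 = 63 doses, giving 273/336 = 81.3%, above the cut. Three consecutive intervals span 78 to 90 days, giving 77.7% to 74.1%.
- A diary lost while the subject is off drug holds no doses and changes nothing.

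**After limiting both sides to documented intervals:** with three diaries lost, nine intervals remain, with 9 × 28 = 252 doses over 252 days. Grams per dose returns to 1.00 times the true value, and compliance over diary-covered days is 252/252 = 100%.

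**The case against.** The strongest reply has four parts.

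1. **The SAP has no partial-diary rule, so zero doses for a lost diary is an inference.** That is correct, and a reader should not take it as an explicit instruction. It is still what the formulas give if followed as written, since nothing reduces grams or expected days when a diary is missing. The treatment-period definitions cited from SAP Section 10.1 are not visible in the public text. They bear on compliance, whereas grams per dose is defined over the whole study.

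2. **Counting undocumented doses as not taken is a consistent, conservative choice.** This stands for compliance. It matches diary-based assessment in the protocol and the SAP's treatment of non-computable compliance as below 80%. Restricting compliance to diary-covered days would overstate it if non-adherent subjects lose more diaries. The defence does not extend to grams per dose, where the undercount inflates the result.

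3. **The effect on the study is small.** This largely stands. There is no statistical testing, the only analysis set is all enrolled subjects, and in the visible text the 80% flag excludes nobody. Total expected days and total grams do not use diary counts. The sample size rationale and the interim trigger do not refer to documented doses. Medians are reported beside means.

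4. **The frequency is unknown, and lost diaries may go with lost tubes.** This also stands. A reader might infer that the trial's average grams per dose is biased upward overall; the documents do not support that. Lost tubes offset the inflation, and no loss rate is given.

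**Conclusion.** The point holds for grams per dose. As written, SAP Section 13.1 gives a mismatched ratio for any subject who loses some on-treatment diaries and returns the tubes for those weeks. The inflation runs from 1.09 times for one of 12 diaries lost to 8.6 times for 11, assuming continuous 48-week treatment, perfect dosing, nominal intervals and zero doses for a lost diary.

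For compliance the point is narrower. A reader might infer that any adherent subject who loses three of 12 diaries is labelled non-compliant. That holds only when the lost diaries fall in treatment periods and the intervals are near nominal length. Three is not a general threshold either: one lost diary of four treated intervals is enough. The convention itself is defensible; what is missing is a display of how much of any shortfall is missing documentation.

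The consequence is confined to descriptive exposure and compliance summaries. A correction is worth making because the formula gives a wrong value and the data to correct it are already collected.

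**What to change.** In SAP Section 13.1:

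1. **Grams per dose.** Compute it only over visit intervals that have both a returned diary and weighed returned tubes, using the grams and the home and clinic doses of those intervals alone. Trace weights at tube level, because forgotten tubes may come back at a later visit and unopened tubes may be re-dispensed once. Report how many subjects and intervals are excluded.
2. **Partial diary return.** State the rule explicitly for doses and for compliance.
3. **Compliance.** Keep the present calculation, with undocumented doses counted as not taken, as the conservative main figure. Show on-treatment diary-missing days in their own row, and add compliance over diary-covered days as a sensitivity line.

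The cost is SAP wording and an interval-level derivation from existing diary and drug accountability records; no new data are collected. The downside is that some subjects contribute fewer intervals and those kept may be a selected subset, which is why the exclusions should be counted.

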13.2 Adverse Events

All AE summaries will be restricted to TEAEs. For rollover subjects, all AEs reported in this study will be considered as TEAEs except for those AEs resolved prior to the Visit 1 date in this study. For direct-enrolling subjects, all AEs that start after the first dose of study drug will be

considered a TEAE. Verbatim terms in the eCRFs will be mapped to PTs and SOCs using MedDRA, Version 24.0.

Imputation of start and end dates of AEs

To calculate duration of AEs, the following rules will be used where applicable to impute partial or completely missing start dates or end dates:

- If only the day is missing for a start date, the 1st of the month will be imputed. If the new estimated date falls before the Visit 1 date, while the known month and year match the month and year of the Visit 1 date, the date of Visit 1 will be used as the new estimated date.
- If only the day is missing for an end date, the last day of the month will be imputed. If the new estimated date falls after the date of last study visit, the date of last study visit will be used as the new estimated date.
- If both the day and the month are missing for a start date or end date, no imputation will be used, and the duration will not be calculated.
- If the start date or end date is completely missing, duration will not be calculated.

For AEs ongoing at the end of the previous studies, duration will be computed using the DMVT-505-3103 Visit 1 date as the AE start date.

Imputation of missing relationship and/or missing severity

If relationship to treatment is missing, the event will be conservatively treated as related to study drug.

If severity is missing and the AE is reported as serious and fatal, severity will be imputed as CTCAE=5. If severity is missing and the AE is reported as serious and not fatal, severity will be imputed as CTCAE=4. If severity is missing and the AE is not reported as serious, severity will be imputed as CTCAE=3.

All TEAEs will be listed by subject, detailing the verbatim term given by the investigator, PT, SOC, onset date, end date, ongoing at the end of parent studies (Y/N), duration (days), CTCAE grade, outcome, relationship to study drug, action taken with study drug, other action taken to treat the event, AE of special interest (AESI) (Y/N), seriousness and criteria for seriousness.

AEs resolved prior to the Visit 1 date, Serious TEAEs, TEAEs leading to study drug discontinuation, TEAEs leading to study discontinuation and TEAEs related to study drug will also be listed separately. The following AESIs will be identified and listed separately: contact dermatitis, follicular event, and headache.

The frequency and percent of subjects with AEs will be summarized as incidence rates of:

- Any AE

The frequency and percent of subjects with TEAEs will be summarized as incidence rates of:

- Any TEAE
- Any TEAE excluding those ongoing at the end of the previous studies
- Any TEAE ongoing at the end of the previous studies
- Any treatment-emergent AESIs
- Any treatment-emergent AESIs excluding those ongoing at the end of the previous studies
- Any treatment-emergent AESIs ongoing at the end of the previous studies
- Any treatment-related TEAE
- Any TEAE leading to study drug discontinuation
- Any TEAE leading to study discontinuation
- Any serious TEAE
- Death
- Treatment-related serious TEAE
- Serious TEAE leading to study drug discontinuation
- Serious TEAE leading to study discontinuation
- TEAE (COVID-19)

TEAEs will be sorted alphabetically by SOC and decreasing PT frequency in the Total (Overall) group for the following:

- All TEAEs
- All TEAEs by maximum CTCAE grade

- All TEAEs by maximum causality (not related, related) to the study drug
- All TEAEs excluding those ongoing at the end of the previous studies
- All TEAEs ongoing at the end of the previous studies
- All treatment-related TEAEs
- All TEAEs leading to study discontinuation
- All TEAEs leading to study drug discontinuation
- All serious TEAEs
- All serious TEAEs leading to study discontinuation
- All serious TEAEs leading to study drug discontinuation

All TEAEs and all serious TEAEs will also be summarized by SOC (alphabetical order) and PT (descending order) for the following subgroups:

- Age (2-6 yrs, 7-11 yrs, 12-17 yrs, ≥ 18 yrs)
- Sex
- Race (White, Asian, Black or African American and Other)

TEAEs by maximum CTCAE grade, TEAEs by maximum causality, TEAEs leading to study drug discontinuation and TEAEs leading to study discontinuation, will be summarized by SOC (alphabetical order) and PT (descending order) for the Age subgroup.

Furthermore, TEAEs will be categorized by day of onset among the following 4 categories:

- ≤ 12 weeks
- > 12 to ≤ 24 weeks
- > 24 to ≤ 48 weeks
- > 48 weeks.

For each of these categories, TEAEs will be summarized by SOC in alphabetical order and PT in descending order of frequency. TEAEs ongoing at the end of the previous studies will be considered in the first category (i.e., day of onset ≤ 12 weeks).

At each level of summarization, a subject will be counted once if he/she reported one or more events. The severity of TEAEs and relationship to study drug will be summarized in a similar manner. For summaries of relationship to study drug, a subject will be classified according to related or not related. For summaries of TEAE CTCAE grade, a subject will be classified according to the worst grade.

For treatment-emergent AESIs, summarization will be more extensive, reflecting the more detailed information collected. Information summarized will include number of events per subject, earliest onset day, duration (in days), causality, grade and seriousness of AESIs, outcome, actions taken, assorted physical characteristics of the AESIs, and demographic/baseline characteristics and vIGA-AD™ status of the subjects experiencing them. Each type of AESI will be summarized separately. If a subject has more than one treatment-emergent occurrence of an AESI, the subject's maximum duration, highest levels of causality and seriousness, maximum grade and generally the most extreme level of each characteristic will be summarized. If an AESI was ongoing at end of study (EOS), it will not be included in the duration summary. AESIs ongoing at the end of previous studies will also be included in the summary.

A Kaplan-Meier figure will be generated for each AESI of time to first event for events starting during the study. Time to first onset will be computed as Onset Date of First Occurrence – Date of Visit 1 + 1 if onset date is on or after visit 1 date. Otherwise, time to first onset will be computed as Onset Date of First Occurrence – Date of Visit 1. Subjects not experiencing the AESI will be censored at the date of study completion or discontinuation. AESIs ongoing at the end of the previous studies will not be included.

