3.1 Overall Design

This is an open-label, long-term multicenter, study to evaluate the safety and efficacy of topical tapinarof cream, 1% in subjects with AD. Subjects in this study will have either: a) completed treatment with tapinarof or vehicle in one of two Phase 3 pivotal safety and efficacy studies, DMVT-505-3101 or DMVT-505-3102, and rolled over into this study; b) completed treatment with tapinarof in the Phase 2 maximal use PK study, DMVT-505-2104, and rolled over into this study; or c) enrolled directly into this study. This study will consist of up to 48 weeks of treatment and a 1-week safety follow-up period.

At the completion of the Week 8 visit of study DMVT-505-3101 or study DMVT-505-3102 or the Day 28 visit of study DMVT-505-2104 (Baseline [Day 1] in this study), all eligible subjects will be offered enrollment in this OL-LTE study. Approximately 125 additional pediatric subjects ages 2 to < 18 years who are not eligible for participation in the Phase 3 pivotal studies (DMVT-505-3101 or DMVT-505-3102) will be enrolled directly into this OL-LTE study. Study visits during the treatment period for all subjects will occur every 4 weeks (\pm 3 days). Unscheduled visits may occur, as needed. Subjects who withdraw from the study before Week 48 will return to the study site for an Early Termination visit. The total duration of subject participation in this study will be approximately 49 weeks for rollover subjects (Baseline to Follow-Up) and approximately 53 weeks for direct-enrolling subjects (Screening to Follow-Up).

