6.2 Safety Assessments

6.2.1 Adverse Events

All AEs and SAEs will be collected from the time the subject signs the informed consent form (ICF) until the final visit/contact with the subject. AEs that began during the parent study and were ongoing at the end of that study will be reported as ongoing AEs. Additional safety information, including the definition of an AE and the methods for recording, evaluating, and assessing causality of AEs and the procedures for completing and transmitting SAE reports are provided in [Section 8](#).

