10.4.3 Safety Analyses

The ITT Population will be used in the analysis of safety data. Summaries will be presented overall and by the following categories: received tapinarof treatment in either DMVT-505-3101 or DMVT-505-3102; received vehicle treatment in either DMVT-505-3101 or DMVT-505-3102; received tapinarof treatment in DMVT-505-2104; and enrolled directly into DMVT-505-3103.

The number and percent of subjects with TEAEs will be summarized by system organ class, and preferred term for all TEAEs, all TEAEs considered by the Investigator to be related to study drug, all SAEs, all TEAEs leading to study drug discontinuation, and all TEAEs leading to study discontinuation. TEAEs will be defined as follows:

- For rollover subjects, all AEs reported in DMVT-505-3103 will be considered to be a TEAE except for those AEs ongoing at the end of the parent study (DMVT-505-3101, DMVT-505-3102, or DMVT-505-2104) but resolved prior to the Visit 1 date in DMVT-505-3103.
- For subjects enrolled directly into DMVT-505-3103, all AEs that start after the first dose of study medication will be considered to be a TEAE.

Data listings will be provided for subjects who discontinued the study due to an AE and for subjects with an SAE.

Laboratory values will be classified as normal, low or high based on normal ranges supplied by the laboratory. Changes from Baseline in abnormality status will be summarized using shift tables. For quantitative laboratory measures, observed values and changes from Baseline will be summarized descriptively by visit.

Observed vital sign values (systolic and diastolic blood pressure, pulse rate, and body temperature) and change from Baseline in vital signs will be summarized similarly to the laboratory values.

LTS scores will be summarized by visit for subject (or caregiver) overall assessment and Investigator overall assessment separately.

• [REDACTED]
[REDACTED]
[REDACTED]
[REDACTED]
[REDACTED]
[REDACTED]
10.4.5 [REDACTED]
[REDACTED].

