Rollover subjects in this study will begin treatment based on their validated Investigator Global Assessment for Atopic Dermatitis (vIGA-ADTM) score from the final visit in one of the three aforementioned studies (DMVT-505-3101, DMVT-505-3102, or DMVT-505-2104). Subjects entering with a vIGA-ADTM ≥ 1 will receive treatment with tapinarof cream, 1% once daily (QD) until they achieve a vIGA-ADTM score of 0, at which time treatment will be discontinued and subjects monitored for maintenance of disease control (i.e., the extent of the remittive effect). If/when disease worsening occurs, as evidenced by a flare to vIGA-ADTM ≥ 2 , treatment will then be re-initiated and continued until a vIGA-ADTM of 0 is achieved. Subjects entering with a vIGA-ADTM of 0 will have treatment discontinued beginning at the Baseline visit and will be monitored for maintenance of the remittive effect. If/when disease worsening occurs, as evidenced by a vIGA-ADTM ≥ 2 , treatment will then be re-initiated and continued until a vIGA-ADTM of 0 is achieved. This treatment and re-treatment pattern of use will be continued until the end of the study (i.e., subjects may receive study treatment up until the Week 48 visit).

Subjects enrolling directly into this study will receive treatment QD with tapinarof cream, 1% beginning at Baseline and continue treatment until they achieve a vIGA-ADTM score of 0, at which time treatment will be discontinued and subjects monitored for maintenance of the remittive effect. If/when disease worsening occurs, as evidenced by a flare to vIGA-ADTM ≥ 2 , treatment will be re-initiated and continued until a vIGA-ADTM of 0 is achieved. This regimen of treatment and re-treatment will continue until the end of the study (i.e., subjects may receive study drug up until the Week 48 visit).

Study drug will be dispensed to subjects or their caregivers, applied during the clinic visits, and applied at home between clinic visits as instructed by site personnel. Subjects or their caregivers will be instructed to apply study drug QD to all affected areas, including newly appearing lesions and lesions/areas that improve during the study until a vIGA-ADTM of 0 is achieved. Once a vIGA-ADTM of 0 is achieved, the treatment period ends. If/when disease worsening occurs, and treatment is re-initiated at a vIGA-ADTM of ≥ 2 , all lesions currently present and any new lesions that occur during the new treatment period should be treated.

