7. NOTATION OF TREATMENT GROUPS AND VISITS

Notation of treatment groups

The following notation of **treatment groups** will be used throughout the report:

Full Notation (as used in the study protocol)	Notation Used Throughout All Tables, Listings, and Figures
Tapinarof Cream 1%, rolling over from DMVT-505-3101 or DMVT-505-3102	Tapinarof Cream 1% (Pivotal)
Vehicle Cream, rolling over from DMVT-505-3101 or DMVT-505-3102	Vehicle Cream (Pivotal)
Tapinarof Cream 1% and Vehicle Cream (Pivotal)	Total (Pivotal)
Tapinarof Cream 1%, rolling over from DMVT-505-2104	Tapinarof Cream 1% (2104)
Tapinarof Cream 1%, enrolling directly into DMVT-505-3103	Tapinarof Cream 1% (Direct-Enroll)
Tapinarof Cream 1%	Total (Overall)

Visit terminology

Visit	Notation Used Throughout All Tables, Listings, and Figures
Screening, Days -30 to Day -1, Visit V0	Screening
Baseline, Day 1, Visit V1	Baseline
Week 4, Day 29 (± 3 days), Visit V2	Week 4
Week 8, Day 57 (± 3 days), Visit V3	Week 8
Week 12, Day 85 (± 3 days), Visit V4	Week 12
Week 16, Day 113 (± 3 days), Visit V5	Week 16
Week 20, Day 141 (± 3 days), Visit V6	Week 20
Week 24, Day 169 (± 3 days), Visit V7	Week 24
Week 28, Day 197 (± 3 days), Visit V8	Week 28
Week 32, Day 225 (± 3 days), Visit V9	Week 32
Week 36, Day 253 (± 3 days), Visit V10	Week 36
Week 40, Day 281 (± 3 days), Visit V11	Week 40
Week 44, Day 309 (± 3 days), Visit V12	Week 44
Week 48, Day 337 (± 3 days), Visit V13 (End of Treatment)	Week 48
Week 49, Day 344 (± 3 days), Visit V14 (End of Study/Follow-up)	Week 49

Note: A phone call to review study drug application instructions, if applicable, and to record AEs and concomitant medication use will occur on Week 2, Day 15 (± 3 days).

Analysis visits

Study days are measured from baseline (Visit 1) in the extension study. Study days corresponding to measurements are calculated as:

- Assessment date – date of baseline (Visit 1) + 1 if assessment date is on or after the date of baseline (Visit 1)
- Assessment date – date of baseline (Visit 1) if assessment date is before the date of baseline (Visit 1)

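### The rollover TEAE rule depends only on Visit 1, so for subjects coming from vehicle it counts AEs that began before any tapinarof dose as treatment-emergent

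*SAP*

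**What the plan says.** The SAP sets two TEAE rules in section 13.2. For rollovers: "For rollover subjects, all AEs reported in this study will be considered as TEAEs except for those AEs resolved prior to the Visit 1" date. For the others: "For direct-enrolling subjects, all AEs that start after the first dose of study drug will be" treatment-emergent.

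Protocol 10.4.3 has the same pair. Its rollover rule begins "all AEs reported in DMVT-505-3103 will be considered to be a TEAE except for those AEs ongoing at the end of the parent study", and the sentence goes on to limit that exclusion to events resolved before Visit 1. Its direct-enroller rule is "all AEs that start after the first dose of study medication will be considered to be a TEAE".

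Four other provisions determine what the rollover rule captures:

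- Protocol 3.1 admits subjects who "completed treatment with tapinarof or vehicle in one of two Phase 3 pivotal safety and efficacy studies", so some rollovers come from vehicle.
- Protocol 6.2.1 brings parent-study events into this study's data: "AEs that began during the parent study and were ongoing at the end of that study will be reported as ongoing AEs".
- SAP 4 says that rollovers who enter with vIGA-AD 0 "will have treatment discontinued beginning at the Baseline visit and will be monitored for maintenance of the remittive effect". They start drug only on a flare to vIGA-AD 2 or more.
- SAP 8 and 13 base safety on every enrolled subject, dosed or not. SAP 9.1 counts those who apply any study medication separately from those enrolled.

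SAP 7 gives vehicle rollovers a column of their own ("Vehicle Cream, rolling over from DMVT-505-3101 or DMVT-505-3102") and also pools them into Total (Pivotal) and Total (Overall). The full notation of the last is Tapinarof Cream 1%.

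**The concern.** Within this program, direct enrollers and vehicle rollovers both first meet tapinarof in DMVT-505-3103. Direct enrollers get a rule tied to that first dose. Vehicle rollovers get a rule that makes sense for people already on tapinarof when they arrive: it has no onset condition, no dose condition and no split by parent treatment.

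Safety is the first-listed objective. A TEAE column for subjects switched from vehicle should describe what followed the switch. As written, it can mix in events from the vehicle period and from a drug-free period, and the pooled columns then carry them under a tapinarof label.

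**Working it through.** The documents state no figure on this point. The check is to apply each written rule to every possible timing of an AE in a vehicle rollover.

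| AE in a vehicle rollover | Rollover rule (as planned) | First-dose rule (as for direct enrollers) |
|---|---|---|
| Began on vehicle, resolved before Visit 1 | not a TEAE | not a TEAE |
| Began on vehicle, ongoing at Visit 1 | **TEAE** | not a TEAE |
| Entered clear; onset after Visit 1, before first tapinarof dose | **TEAE** | not a TEAE |
| Entered clear, never flares, never dosed; onset after Visit 1 | **TEAE** | not a TEAE |
| Onset after first tapinarof dose | TEAE | TEAE |

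The rules differ in the middle three rows. Row 2 is kind (a); rows 3 and 4 are kind (b). Subjects who enter with vIGA-AD 1 or more start drug under supervision at Baseline (Protocol 7.2.1), so for them kind (b) shrinks to any AE between consent and application on Day 1.

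**What SAP 13.2 already does about kind (a):**

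- The TEAE listing flags each event as ongoing from the parent study or not.
- The any-TEAE and any-AESI overview rows, and the all-TEAE table by system organ class and preferred term, are repeated with carried-over events removed and again with only those events.
- The AESI Kaplan-Meier figures leave them out.

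**Where kind (a) remains, with no version that removes it:**

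- The treatment-related, maximum-grade and maximum-causality tables.
- The age, sex and race subgroup tables.
- The detailed AESI summary, which includes carried-over AESIs and reports each subject's most extreme value. A vehicle-onset event can therefore supply the grade or causality shown. Its duration is counted from Visit 1, not from its true start.
- The onset-period table, which puts carried-over events in the category up to 12 weeks although they began before Visit 1.

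The serious and discontinuation tables also lack such a version, but eligibility largely protects them. Protocol 4.3, exclusion 3, bars rollovers who had a treatment-related SAE, or an AE that led to permanent discontinuation, in the parent study. A serious but unrelated event still ongoing at Visit 1 could enter.

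**Kind (b):** no visible planned table separates these events. The AESI Kaplan-Meier figures do not help, because their clock starts at Visit 1 and not at first tapinarof.

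**The case against.** The strongest reply is that the plan over-counts and hides nothing. The rule is the same in protocol and SAP, the study is descriptive, vehicle rollovers have their own column, and carried-over events are shown with and without in the headline summaries. That stands for those summaries. It does not reach the tables listed above, and it does not touch kind (b).

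Several stronger readings are tempting, and the documents do not support them:

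- *That the headline TEAE rate is inflated without remedy.* Suppose 50% of vehicle rollovers have a post-tapinarof TEAE and, independently, 5% to 15% enter with an ongoing AE (all assumed values). The any-TEAE row then reads 1 − 0.50 × 0.95 = 52.5% to 1 − 0.50 × 0.85 = 57.5%. But the planned row without carried-over events would read 50% in the same example.
- *That the number affected can be taken as a vehicle share of 836.* The 836 includes DMVT-505-2104 rollovers, who all received tapinarof. The documents give no allocation ratio for the pivotal studies and no AE rate.
- *That events judged related on blinded vehicle will enter the tapinarof-related table.* These documents do not state the blinding of DMVT-505-3101 and DMVT-505-3102, or whether causality is reassessed when an event is carried over. For never-dosed subjects, Protocol 8.2.2 makes a related judgement depend on timing relative to drug administration, which limits entry to that table.
- *That the plan spoils a comparison of the two groups new to tapinarof.* No comparison is planned. Direct enrollers are all under 18 and had failed the pivotal BSA or vIGA-AD criteria, so the groups differ in any case.
- *That protocol and SAP contradict each other.* They do not; they share one weak definition.

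**Conclusion.** The point holds as a weakness of definition. For vehicle rollovers, the rule labels as treatment-emergent AEs that began on vehicle and AEs that precede any tapinarof dose in this study. Kind (a) is partly mitigated. Kind (b) is not, but it needs a vehicle rollover who enters clear (apart from the short Day 1 window), and that group may be small.

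No size can be derived: the documents give neither the number of vehicle rollovers, nor how many enter clear, nor how many enter with an ongoing AE. The effect is on descriptive incidence and on the detail of the AESI tables; no test is affected. The conclusion assumes that no redacted text adds a separate table for pre-dose events, and that vehicle rollovers had no tapinarof before this study. The parent eligibility criteria, which would settle the second assumption, are not in these documents.

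**What to change.** In SAP 13.2:

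1. Keep the current rule for rollovers who received tapinarof in the parent study.
2. For vehicle rollovers, use the direct-enroller rule unchanged: onset after the first tapinarof dose in DMVT-505-3103.
3. List and tabulate carried-over and pre-first-dose AEs in vehicle rollovers separately as non-treatment-emergent, including those of never-dosed subjects.
4. Record the departure from Protocol 10.4.3 in SAP 14, which now reports no changes.

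Add a clause for worsening in grade only if the CRF records dated grade changes; the planned listing shows one CTCAE grade per event. If it is added, apply it to vehicle rollovers and direct enrollers alike, so that the two groups share one definition.

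The inputs should already exist: parent arm defines the columns (SAP 7), onset date is listed (SAP 13.2), and dosing is recorded in diary and clinic records (Protocol 5.4, SAP 13.1). The SAP's partial-date rules are written for AE duration and refer to Visit 1, so one sentence should say how they apply to first dose. The cost is one derivation flag, one extra listing or table, and slightly lower TEAE counts in the vehicle-rollover and total columns.
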